**7.3 Exclusion criteria**

**Patients meeting any one of the following criteria are not eligible for the study:**

**Medical Status**

1. Patient with LCAT mutation will be excluded
2. Patient who experienced a cardiovascular event within 6 months prior to the onset of screening
3. Patient who experienced stroke or other cerebrovascular event within 1 year prior to the onset of screening
4. Patient with triglycerides level above 500 mg/dL
5. The patient has evidence of clinically significant, uncontrolled or unstable cardiovascular, renal, hepatic (incl. AST or ALT at or above 3x ULN, or bilirubin at or above 2x ULN), gastrointestinal, hematologic, immunological, neurological, endocrine, metabolic or pulmonary disease (as determined by medical history, clinical laboratory or ECG results, or physical examination) or any other medical disorder that would increase the risk associated with taking study medication or would confound the interpretation of study results
6. Patients with a body mass index (BMI)  $<$  17 kg/m^2 or  $>$  40 kg/m^2
7. Patients with severe anemia defined as hemoglobin level below or equal to 10 g/dL
8. Any clinically significant abnormal laboratory data, vital signs, physical examination at screening or baseline, which in the opinion of the investigator, would interfere with safety assessments

9. Clinically significant electrocardiogram (ECG) abnormality at screening, including sinus bradycardia (resting heart rate < 50 beats per minute), 2nd or 3rd degree atrioventricular block, prolonged QTc (QTcF  $\geq$  450 ms in males and  $\geq$  470 ms in females) history of congenital long QT syndromes, or risk of Torsades de Pointes because of family history of sudden death, etc.
10. Positive result on the serum pregnancy test or are breast feeding at screening, or intend to become pregnant during the course of the trial
11. Male intending to father a child during the study
12. Likely to be unreliable as a study participant based on the Investigator's (or designee's) knowledge of the patient (e.g., alcohol or other drug abuse, inability or unwillingness to adhere to the protocol, or psychosis)
13. Symptomatic (NYHA Class II or greater) congestive heart failure requiring and persisting despite appropriate medical treatment
14. Uncontrolled blood pressure: systolic blood pressure  $\geq$ 160 mmHg and/or diastolic blood pressure  $\geq$ 100 mmHg at screening or any other pre-randomization visit
15. Uncontrolled diabetes mellitus defined as HbA1c  $>$ 10%
16. Unexplained creatine phosphokinase level  $>$  3 times the ULN
17. History of malignancy during the 3 years prior to screening, with the exception of basal cell carcinoma of the skin
18. Current alcohol or drug abuse or history thereof within 5 years prior to screening
19. Contraindication to MRI scanning such as imbedded metal (e.g., shrapnel), implanted metal objects (e.g., pacemaker), claustrophobia
20. Participated in any investigational study or taken an investigational drug within 30 days (or 5 times the half-life of the investigational drug, whatever is longer)
21. Ever received CER-001 within 6 month from the onset of screening
22. Medically non-compliant in the management of their disease in the investigator's opinion

#### **7.4 Concomitant Treatments**

Any medication the patient takes, other than study drugs specified by the protocol, is considered a concomitant medication. All concomitant medications must be recorded in the electronic case report form (eCRF).

#### **7.5 Prohibited Medication**

There are no excluded medications other than any other investigational drugs.

#### **7.6 Permitted Medication**

All medications that are considered medically necessary for maintenance of patient health are permitted during the study. Details of their use must be recorded on the concomitant medication page of the eCRF.

## 7.7 Monitoring of Patient Compliance

All study therapy will be administered under direct observation.

# 8 STUDY PROCEDURES

A detailed schedule of assessments by visit is shown in *Appendix A* and *Appendix B* and a detailed description of assessments and procedures during screening, double-blind and open-labeled treatment is given below.

## 8.1 Screening Examination and Eligibility Screening Form

All patients must provide written informed consent before any study specific assessments or procedures are performed. An Eligibility Screening Form (ESF) documenting the investigator's assessment of each screened patient with regard to the protocol's inclusion and exclusion criteria is to be completed by the investigator. A screen failure log must be maintained by the investigator.

### Visit 1

This is the first visit of the study. This visit will be performed after obtaining written informed consent. The investigator will advise the patient on heart healthy diet and life style.

Screening assessments include:

- Informed Consent
- Inclusion/exclusion criteria
- Demographic information
- Smoking status
- Measurement of height and body weight
- Medical history/surgical history and concomitant diseases
- Previous and concomitant treatments
- Physical exam (See Section 8.8.1)
- Vital Signs (See Section 8.8.2)
- Blood Pressure and Heart Rate
- ECG (See Section 8.8.3)
- Serum biochemistry (See Section 8.8.4)
- Hematology and coagulation (See Section 8.8.4)
- Urinalysis (See Section 8.8.4)
- Fasting lipid profile (See Section 8.9), including Apolipoprotein profile.
- Anti-ApoA-1 antibody (See Section 8.8.5)
- Markers of inflammation, oxidation, lipid metabolism and CV risk (See Section 8.10)
- Serum pregnancy test in female patients (See Section 11.8)
- FSH (only for women whose last menstrual period was between 6 and 12 months before screening)
- Fasting blood glucose and HbA1c
- Creatinine and/or BUN testing to determine GFR

Patient must have fasted (ie not to take any food or liquids other than water) for 8 hours prior to blood sampling.

A DNA sample will be taken ONLY for determination of the presence of HDL gene mutations specifically for ABCA1 and/or ApoA-1 mutation(s) to ensure that the patient was to satisfy all inclusion and exclusion. Genotyping will be performed at the Robarts Research Institute, London, Canada.

**Following visit 1, if a patient is eligible according to all of the inclusion and exclusion criteria, he/she will be instructed to come in fasted for the randomization visit 2.**

## **8.2 Procedures for Enrollment of Eligible Patients and Assessment at Visit 2**

Once a patient has fulfilled all inclusion and exclusion criteria, he/she will be randomized at visit 2 to receive CER-001 or placebo using an interactive voice response system (IVRS/IWRS). The investigator/designee will contact the IVRS/IWRS to randomize a patient for this study and will be given a patient number and a randomization number. The investigator or designee will use the eCRF with the assigned patient number and the IVRS/IWRS will automatically download the treatment allocation and randomization number as well as the patient number for the patient into the eCRF.

The following assessments will be performed at visit 2 (V2):

- Physical exam (See *Section 8.8.1*)
- Blood Pressure and Heart Rate
- Measurement of weight and vital signs (See *Section 8.8.2*)
- ECG (See *Section 8.8.3*)
- Blood samples for
  - Hematology and coagulation (See *Section 8.8.4*)
  - Serum chemistry (See *Section 8.8.4*)
  - Fasting lipid profile (See *Section 8.9*)
  - Markers of inflammation, oxidation, lipid metabolism and CV risk (See *Appendix A*)
  - Fasting blood glucose and HBA1c
  - Protein biomarker assessment
- Urinalysis (See *Section 8.8.4*)
- Pregnancy test
- Previous and concomitant medication
- Adverse events
- Creatinine and/or BUN testing to determine GFR

Patient must have fasted (ie not to take any food or liquids other than water) for 8 hours prior to blood sampling.

The first 3T-MRI and the first FDG-PET/CT scan assessing the carotid and femoral artery will be optimally performed at this visit prior to the first infusion.

After all assessments have been performed the patient will be administered the first infusion as described in Section 9.6.

He/she will stay for an additional hour after the infusion to ensure completion of the overall examination. A blood sample will be drawn two hours after initiation of the infusion to assess the pharmacokinetics of the study drug.

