### 9.3 Placebo

Placebo, standard sodium chloride solution, is provided as a 250 mL solution for infusion similar in volume to the active treatment solution study.

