### 9.5 Medication Dispensing and Administration

The Investigator will administer the study medication only to patients included in this study following the procedures set out in the study protocol. Each patient will be given only the study medication assigned by the randomization system. All dispensing will be documented in the eCRF and other study drug records.

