## **9.8 Investigational Product Accountability**

The Investigator or designee must maintain accurate and adequate records including dates of receipt and return of drug shipments, lot number (if available), and quantities received/returned, as well as dates and amounts administered, and returned by the study site.

All vials, empty, partial, or full, must be returned. The study site must ensure that unused supplies remain in their original containers as provided by Catalent Pharma Solutions for Cerenis Therapeutics and that the label is intact and unobiterated. The “Clinical Returns Authorization Form” contains a specific return shipping address and instructions.

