## **9.11 Maintaining the Blind**

Study drug will be dispensed by an unblinded Study Pharmacist or designee who will be unblinded as described in Section above (Section 9.10). The study patients, Investigator, sponsor and study site personnel and site monitors will remain blinded to the treatment. During the study, and prior to database lock, no lipid profile data will be reported to the Investigator or to the Sponsor. Data will be reviewed in a blinded manner.

Randomization list is kept strictly confidential, accessible only to authorized persons, until the time of unblinding. It is the responsibility of the Pharmacist to maintain the blind throughout the study.

The randomization code may be broken if an emergency situation arises that in the Investigator's opinion requires the knowledge of the code (for example, life threatening situation or necessity to know the product administered to provide with the best medical care). The investigator must do his/her very best to contact the Sponsor before unblinding the code using an Interactive Web Response System (IWRS). Date, time, and reason(s) for breaking the code must be recorded by the Investigator in IWRS.

At the conclusion of the trial, the occurrence of any emergency code breaks will be verified after return of all code break reports and unused drug supplies to the packaging supplier.

The CRO mandated for pharmacovigilance reserves the right to break the blind for SAEs which are considered as related to the study drug and unexpected, which could require an expedited report to the regulatory authorities.

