After obtaining written informed consent, completing screening procedures, and ensuring the patient meets all of the inclusion criteria and none of the exclusion, the patient will be randomized. Stratification according to the genetic mutation (ABCA-1/ApoA-1) will be done to ensure appropriate balanced distribution of the mutations across treatment groups. The patient will be randomized to receive 29 infusions of either active drug or placebo using a 2:1 randomization scheme.

5. Unblinding

Unblinding will be performed by the ICTA PM statistician in charge of the study once database is locked, at the end of the study, with sponsor's agreement.

The unblinding process will be conducted according to ICTA SOP46 ("Randomization and unblinding"). ICTA Quality Assurance department will give the CD-Rom containing the randomization number and the corresponding randomization treatment to the statistician. The database will then be imported in the statistical database of the study. A 100% review of the imported data will be performed by the statistician, compared to initial data provided in the CD-Rom.

6. Populations to be analysed

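### Protocol 8.2 sends each patient's treatment allocation into the eCRF that blinded staff use, against Protocol 9.11 and SAP section 5, and no text restricts who can read it

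*Protocol*

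**What the plan says.** Protocol 8.2 describes randomisation at visit 2. The investigator or designee contacts the IVRS/IWRS and "will be given a patient number and a randomization number". Then "The investigator or designee will use the eCRF with the assigned patient number", and in the same sentence "the IVRS/IWRS will automatically download the treatment allocation and randomization number as well as the patient number for the patient into the eCRF".

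Protocol 9.11 sets the blind: "The study patients, Investigator, sponsor and study site personnel and site monitors will remain blinded to the treatment". It also keeps the randomization list confidential until unblinding, and has an emergency code break made in the IWRS with date, time and reason recorded. Protocol 9.10 places unblinding of the data after the last patient's final visit and database lock.

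SAP section 5 agrees with that order: "Unblinding will be performed by the ICTA PM statistician in charge of the study once database is locked". The statistician receives the randomization numbers and matching treatments on a CD-Rom from the CRO's Quality Assurance department.

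Three drug-handling rules also bear on the point. Protocol 9.5 says "All dispensing will be documented in the eCRF and other study drug records". Protocol 9.8 gives accountability records to the investigator or designee and adds "All vials, empty, partial, or full, must be returned". Active drug comes as frozen 20 mL vials (Protocol 9.2 and 9.6), while Protocol 9.3 says "Placebo, standard sodium chloride solution, is provided as a 250 mL solution for infusion".

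**The concern.** The eCRF is the working record of people who are meant to be blinded. Site staff enter data in it, and sponsor and CRO representatives review it (Protocol 16.1 and 16.4). A rule that writes the arm into that record, with no stated restriction, puts the code where it should not be before lock.

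The exposed steps are those that rest on judgement:

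- Safety and tolerability over 24 weeks is one of the two primary objectives (Protocol 4.1). It depends on the investigator's rating of severity (11.2) and relatedness (11.3), and on interruption and dose-reduction decisions (10.2, 10.3).
- The sponsor and the CRO's statistician and project leader jointly decide the analysis populations before unblinding, and grade each deviation as minor or major (SAP 6.1, 6.2).

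With 30 patients randomised 2:1, about 20 receive CER-001 and 10 placebo. A few judgements made with knowledge of the arm could change the related-event table or the per-protocol set.

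**Working it through.** No arithmetic applies beyond the planned group sizes (30 × 2/3 = 20 and 30 × 1/3 = 10). The check is a comparison of texts.

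1. **Is the arm itself sent, or only a code?** Protocol 8.2 lists three items: treatment allocation, randomization number and patient number. Because the allocation is named beside the randomization number, it cannot simply mean that number. On its ordinary meaning it is the arm.

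2. **Where does it go, and who uses that place?** It goes into the eCRF, and the same sentence has the investigator or designee using it. Protocol 9.11 names the investigator and site personnel as blinded.

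3. **Does any text close the gap?** The safeguards in Protocol 9.10 and 9.11 are the opaque shroud on the infusion container, the unblinded Study Pharmacist, the confidential randomization list and the withholding of lipid results. None refers to the eCRF field. Protocol 16.1 and 16.4, which cover data capture and access, make no exception for it. Lipid results, which could only hint at the arm, are expressly withheld. The arm itself has no equivalent rule.

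4. **Do other provisions assume that the arm is not in the eCRF?** Three do. The investigator is told only the patient and randomization numbers (8.2). An emergency code break must go through the IWRS and leave a record (9.11), which a readable eCRF field would bypass. The arm reaches the statistician on separate media after lock (SAP section 5), a step that would be redundant if the study database already held it.

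5. **Does the SAP settle the conflict?** Its introduction says that it takes precedence over the protocol. But section 5 covers how the statistician obtains the code, not what the IWRS writes to the eCRF. Section 10, which lists changes from the protocol, mentions only the efficacy models.

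6. **Do the dispensing rules also reveal the arm?** Only possibly. A vial-level entry would, because the two products are supplied differently. But Protocol 9.5 does not say that the entry names the product. The administration items in SAP 7.3.2 (prescribed dose, preparation time, start and stop times, volume given) need not show the arm if completed alike in both groups.

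Steps 1 to 4 establish a conflict between a stated rule and the stated blind. Step 6 supports a precaution only.

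**The case against.** The strongest reply is that the documents as a whole intend the arm to be withheld, and that 8.2 is loosely worded. The code-break procedure, the confidential list and the CD-Rom all point that way. The downloaded field might be hidden by user role or stored as a code. This part stands: a reader might infer from 8.2 that blinded staff can certainly see the arm, or that the trial cannot be called double-blind, and the documents support neither. They say nothing about how the field is displayed.

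A reader might also infer that dispensing and accountability records reveal the arm at every infusion, or that Protocol 16.4 sends blinded monitors to read them. That goes too far. The designee in 9.8 may be the unblinded pharmacist, who prepares the drug, receives the shrouded bag back and is responsible for the blind. Section 16.4 is a general clause on monitoring, audit and inspection access.

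The consequence is also limited. The primary imaging endpoint is an MRI measurement reviewed by an imaging expert (8.6.1), and the documents show no route from the eCRF field to that reading. Safety is summarised descriptively (12.3.2), and the per-protocol analysis is a sensitivity analysis (SAP 7.4.1.3.2).

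The reply does not remove the conflict. Section 8.2 gives a positive instruction that contradicts 9.11, and an access control that is written nowhere cannot be verified by a site, an ethics committee or an inspector.

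**Conclusion.** The point holds as a contradiction that must be reconciled. Protocol 8.2 sends the allocation into a system used by people whom 9.11 requires to be blinded, SAP section 5 presumes that the arm is held elsewhere until lock, and no text restricts the field. If the rule were followed literally and the field left unmasked, it would apply to all 30 planned patients from visit 2 and through the 29 double-blind infusions (9 + 20). It would compromise adverse event severity and relatedness ratings and the choice of per-protocol exclusions.

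This rests on reading treatment allocation in its ordinary sense and on the absence of any stated restriction. It is not a finding that the blind was broken. No sample size, power or alpha figure changes.

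**What to change.** **Protocol 8.2.** State that the IVRS/IWRS transfers only the patient number, randomization number and randomization date to the eCRF. The allocation stays in the IWRS. Before lock it is available only to the unblinded Study Pharmacist and through routes that the documents already provide: the IWRS emergency code break, pharmacovigilance unblinding of related unexpected SAEs (both in 9.11), and the independent statistician who prepares the unblinded DSMB analyses (SAP section 9). It is merged with the study data after lock, as in SAP section 5. These routes need to be named, because a rule limiting access to the pharmacist alone would contradict them.

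**Protocol 9.5 and 9.8, as a secondary precaution.** State that dispensing entries in the eCRF are arm-neutral (infusion given, start and stop times, volume out of 250 mL), and that vial- and bag-level accountability records are kept by the existing unblinded pharmacist.

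**Cost.** A short protocol wording change, a changed IWRS-to-eCRF transfer setting, and a treatment variable that is merged only after lock. Checking vial accountability before lock would need someone who is not blinded; otherwise it waits until after lock. No analysis changes.

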### **8.3 Clinical Assessments and Procedures during the Double-blind Treatment Period**

Patients will visit the clinic each week for the first 8 weeks and every 2 weeks thereafter until the end of the treatment period (week 48) as described in Appendix A. At each visit, the patient will receive an infusion and will be checked for:

- Adverse events
- Previous and concomitant medications

Complete assessments as described for visit 2 (see *Section 8.2* above) will be performed 4 weeks and 8 weeks after randomization (at visit 6 and visit 10). Thereafter, patients will have complete assessments every 8 weeks until the end of the week 48 treatment period (at week 16, 24, 32, 40 and 48). Unless otherwise specified, blood and urine specimens will be collected prior to study drug dosing.

Markers of inflammation, oxidation, lipid metabolism and CV risk (See *Section 8.10*) will be assessed at baseline, week 8, week 24 and week 48 (end of treatment).

HbA1c assessment will be performed only at baseline (See *Appendix A*).

Anti-ApoA-1 antibody assessment will be performed at week 8, week 24 and week 48 (end of treatment).

Blood samples will be collected for biomarkers assessments at week 24.

A blood sample will also be drawn two hours after initiation of the infusion to assess the PK, at week 24.

Follow-up 3T-MRI will be done at the end of the induction treatment phase (week 8), week 24 and at the end of the overall week 48 treatment period.

Follow-up FDG-PET/CT will be performed only once 24 weeks after randomization.

## 8.4 Clinical Assessments and Procedures during the Open-labeled Treatment Period

Patients will visit the clinic every 2 weeks until the end of the treatment period (week 72) as described in [Appendix B](#). At each visit, the patient will receive an infusion and will be checked for:

- Adverse events
- Previous and concomitant medications

Follow-up 3T-MRI will be done at the end of the open-labeled phase (week 72).

## 8.5 Safety Follow-up

### For patients treated until week 48:

Patients will be instructed to fast prior to the visit. A safety follow-up for all patients will be conducted 4 weeks (+/- 7 days) after the final dose of study medication and will include,

- Physical exam (See Section 8.8.1)
- Blood Pressure and Heart Rate
- Vital signs (See Section 8.8.2)
- ECG (See Section 8.8.3)
- Previous and concomitant treatments
- Adverse Events
- Urinalysis (See Section 8.8.4)
- Blood samples for
  - Serum biochemistry (See Section 8.8.4)
  - Hematology and coagulation (See Section 8.8.4)

### For patients treated until week 72:

A safety follow-up for the patients will be conducted by phone 4 weeks (+/- 7 days) after the final dose of study medication and will include:

- Previous and concomitant treatments
- Adverse Events

## 8.6 Specific Imaging Assessments

### 8.6.1 Assessment of Vascular Structure of the Carotid and Femoral with 3T-MRI

Patients will have 3T-MRI imaging performed at Baseline, Week 8, Week 24, Week 48 and Week 72 (optional) for carotid and femoral Mean Vessel Wall Area (MVWA) and carotid normalized wall index (NVWI) measurements.

The baseline 3T-MRI can be done anytime during the screening period, before the randomization provided all other selection criteria are satisfied.

All images will be collected for their review by an imaging expert, with a window of +/- 7 days around the strict date.

The detailed procedure for performing and collecting of 3T-MRI images will be outlined in the Imaging Manual.

